1. ABSTRACT

The NHLBI strategic plan has highlighted a need to identify strategies to halt the atrial fibrillation (AF) epidemic and reduce its related morbidity and financial burden. The growing rate of AF, with projections of afflicting up to 16 million individuals by the year 2050, is not fully explained by known risk factors, underscoring the need to identify novel triggers. Sleep-disordered breathing (SDB) is common in patients with cardiovascular disease and its attendant hypoxemia and autonomic dysfunction create a milieu that is likely to enhance AF propensity. Thus, SDB may represent a novel target for AF prevention and treatment strategies. Although our prior cross-sectional work has shown a 2-4 fold higher odds of AF related to SDB, these and other reports have *not included* cardiac structural data or autonomic/biochemical measures, and have addressed only arrhythmic events occurring during an overnight sleep study. In this proposal, we will examine paroxysmal AF (PAF), an early stage risk factor for persistent AF, and relevant to this proposal because it occurs prior to extensive cardiac electrical remodeling/fibrosis. PAF provides an ideal setting to investigate the immediate influences of SDB and examine temporal patterns given its intermittent nature. We will perform a case control study with each group matched on important confounders such as age (± 5 years), gender, race (white versus non-white), and obesity ($+/- 2$ kg/m 2) and characterized using detailed collection of overnight sleep study data, echocardiographic measures, biomarkers and 7-21 day continuous ECG monitoring. Cases (PAF, n=150) will be recruited from our local AF clinics, and controls (n=150) from medicine and cardiology clinics. The following existing gaps will be addressed: clarify the extent that respiratory event frequency, apnea subtype (obstructive versus central), and hypoxia are associated with PAF independent of cardiac structural abnormalities (i.e. systolic dysfunction and left atrial enlargement); explore the extent to which cardiac morphology, pathways of inflammation/oxidative stress and autonomic dysfunction mediate the SDB-PAF relationship and identify whether temporal patterns of AF paroxysms differ in patients with SDB.

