Data generated from this research is key for developing new strategies to reduce AF-related morbidity including stroke, heart failure and also death. Expected results will be of high impact given ability to identify and inform future screening and treatment approaches for management and/or prevention of AF and identify key outcomes for clinical trials.

The primary aims of the study are to:

SA 1. Quantify the extent that SDB and its subtypes are associated with PAF. SDB will be assessed by the standard metric: the Apnea Hypopnea Index (AHI) and also Central Apnea Index, Periodic Breathing, Obstructive Apnea Hypopnea Index and % sleep time $<90\%$ SaO $_2$. For each, exposure response relationships and thresholds that confer increased risk for PAF will be defined.

Elucidation of the Influence of Sleep Apnea on Risk of Atrial Fibrillation PI- [name] and [name]

SA 2. Examine PAF burden (defined as frequency of paroxysms over a 24 hour period and average duration of paroxysms) via 7-21 day continuous ECG monitoring relative to SDB in those with PAF.

SA 3. Examine the effects of SDB (AHI \geq 15) treatment for 3 months on PAF burden and also measures of autonomic function, cardiac morphology and biochemical measures in those with SDB and PAF.

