1) Clinical Data. The published relationships between SDB and AF, while in general compelling, have flaws. One well referenced study found a significantly higher prevalence of SDB (by questionnaire) in AF patients, many with established structural

heart disease, than in age-matched controls ⁶⁴. In contrast, another study found a similar prevalence of SDB in AF patients and controls ⁶⁶; close reading suggests that this study was likely under-powered with a control sample potentially biased towards having SDB ⁶⁶. A small case control study matched for age and sex and excluding those with LVEF<50% demonstrated a 3-fold increased adjusted odds of AF in those with moderate to severe SDB, but was limited by not taking into account the contribution of central sleep apnea and also did not include detailed assessment of cardiac structural data or autonomic function measures ⁶⁷. Although data support that effectively treated SDB in compliant patients reduces AF recurrence after cardioversion, the comparison group were those non-compliant with SDB treatment, a group perhaps more likely to engage in other unhealthy behaviors increasing AF recurrence ⁶⁹. There are also conflicting data as to whether SDB predicts procedural failure after AF ablation ^{68, 70}.

2) Epidemiologic Data. We have performed epidemiologic observational studies which have demonstrated statistically significant associations of SDB and AF (odds ratio point estimates of 2-4) even after taking into account a host of potential confounding factors such as age, sex, race, body mass index, and self-reported co-morbidities such as hypertension, diabetes mellitus, cardiovascular disease and heart failure ^{1,2}. A major limitation of these large-scale studies is dependence on self-reported diagnoses and a lack of objective cardiac function data to account for the confounding influence of structural cardiac disease. Even when examining the association of Central Sleep Apnea-Cheyne Stokes Respirations (CSA-CSR) with AF, the directionality is unclear, as CSR-CSA could either predispose to AF development or merely represent a marker of cardiac dysfunction leading to AF. Other limitations include lack of measurement or consideration of markers of autonomic function, systemic inflammation, oxidative stress and consideration of only nocturnal ECG data from the sleep study to ascertain AF.

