SA 1. Quantify the extent that SDB and its subtypes are associated with PAF. This aim will be addressed by fitting conditional logistic regression models that condition on the matched pair. We will separately analyze each SDB variable (primary variable: AHI) to obtain an estimate and 95% CI of the odds ratio of PAF for a 1-unit increase in the SDB exposure. Non-linear effects between SDB and the log odds of PAF will be assessed using restricted cubic splines. Knots for the spline will be based on the SDB threshold at which PAF risk increases. Unadjusted and hierarchical adjusted models will be performed using the covariates listed above.

The secondary exposure variables (e.g. hypoxia, OAHI, CAI, AI) will be considered in separate models.

Exploratory Aim 1a. Cardiac structure, autonomic and biochemical variables (Table 2) will explain a proportion of the SDB and PAF relationship. This aim will be addressed by applying Pearl's mediation formula ¹⁰⁸ to the conditional logistical regression model. This approach will allow a causally sound definition of the mediation effect of a given intermediate variable in the relationship between SDB (defined by AHI) and PAF. The approach involves a model for each mediator (e.g. a general linear model for a continuous mediator) and possibly a random effect to account for clustering due to matching and can be thought of as a generalized structural equations model. This approach will allow us to simultaneously assess multiple mediators and will also allow us to consider AHI as a continuous variable. Each model will be fit using likelihood methods and model fit will be checked using appropriate information criteria. After fitting the overall model, we will obtain, for each mediator, an estimate of the indirect effect (e.g. the portion of the overall effect of SDB on PAF mediated through the intermediate variable). A bootstrap resampling technique will be used to obtain a 95% CI for each indirect effect. If the CI does not contain zero, this will indicate statistically significant mediation.

Exploratory Aim 1b. Explore age interactions in the SDB-PAF relationship. Each conditional logistic regression model will include an interaction between age and SDB to investigate if age is a modifier of the effect of SDB on PAF, i.e. whether the odds ratio of PAF for a 1-unit increase in SDB varies by age.

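### SA1 models the obstructive and central apnea indices only one at a time, so it cannot show which is associated with PAF independently of the other

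*Combined protocol and SAP*

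**What the plan says.** SA1 is worded the same way in sections 9 and 10: "Quantify the extent that SDB and its subtypes are associated with PAF". The abstract adds, after listing the indices, "For each, exposure response relationships and thresholds that confer increased risk for PAF will be defined".

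The method is conditional logistic regression on the matched pair, with one SDB variable per model. AHI is the primary exposure. On the others the plan says: "The secondary exposure variables (e.g. hypoxia, OAHI, CAI, AI) will be considered in separate models". On adjustment it says: "Unadjusted and hierarchical adjusted models will be performed using the covariates listed above". That list covers demographics, body size, medications, devices, cardiac status (including left atrial volume and LVEF), blood pressure, diabetes, lifestyle and activity. It contains no SDB index.

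The abstract describes the gap as the extent to which respiratory event frequency, "apnea subtype (obstructive versus central), and hypoxia are associated with PAF independent of cardiac structural abnormalities". Section 3 faults an earlier small case-control study as "limited by not taking into account the contribution of central sleep apnea". The closing paragraph of section 3 presents the work on obstructive and central apnea as exploration.

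**The concern.** OAHI and CAI are measured in the same person on the same night. If they are correlated, a model holding only one of them picks up part of the other's association with PAF. An odds ratio above 1 for OAHI could then come wholly or partly from central apnea, or the reverse. No planned analysis would reveal this: neither index is adjusted for the other, no contrast between them is specified, and AHI pools both kinds of event.

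At stake is what the study may say about subtype. The abstract expects the results to inform screening and treatment approaches. The protocol itself treats the subtypes differently when it decides who may enter the positive airway pressure phase. A signal credited to the wrong subtype would misdirect later work.

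**Working it through.** **1. The plan's own figure.** Section 10 (Power by aim, SA 1) gives N = 300, two-sided alpha 0.05, PAF probability 0.20 at mean AHI, and an odds ratio of 1.50 per SD of AHI at 80% power (1.60 at 90%). For one continuous covariate, n = (z₁₋α/₂ + z₁₋β)² / [P(1−P)(ln OR)²].

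- OR 1.50, 80%: (1.960 + 0.842)² / (0.16 × 0.4055²) gives 299.
- OR 1.60, 90%: (1.960 + 1.282)² / (0.16 × 0.4700²) gives 298.

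At N = 300 the power is 80.2% and 90.3%, so both figures reproduce. The plan states no power for OAHI or CAI, alone or together.

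**2. Bias in a single-index model.** Neither the OAHI-CAI correlation r nor a CAI odds ratio is in the documents, so both are assumptions. With both indices on an SD scale, an OAHI with no effect of its own shows an odds ratio of approximately exp(r × ln OR_CAI):

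| r | OR_CAI 1.5 | OR_CAI 2.0 |
|---|---|---|
| 0 | 1.00 | 1.00 |
| 0.1 | 1.04 | 1.07 |
| 0.2 | 1.08 | 1.15 |
| 0.5 | 1.22 | 1.41 |

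**3. How often the wrong index is significant.** This was simulated with 150 pairs, 2,000 runs per setting, standard normal exposures and no case-control correlation. Only OAHI was truly associated; under these assumptions the roles of the two indices can be exchanged. Results for CAI in its own model:

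| r | OAHI OR 1.5: CAI significant | median CAI OR | OAHI OR 2.0: CAI significant | median CAI OR |
|---|---|---|---|---|
| 0 | 5.6% | 1.002 | 3.7% | 0.998 |
| 0.1 | 6.3% | 1.037 | 8.6% | 1.074 |
| 0.2 | 11.2% | 1.085 | 22.7% | 1.158 |
| 0.3 | 16.2% | 1.136 | 43.6% | 1.235 |
| 0.5 | 39.0% | 1.222 | 83.6% | 1.409 |
| 0.7 | 68.3% | 1.334 | 98.6% | 1.628 |

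The medians agree with the formula in step 2. With both indices in one model, CAI was significant in 3.9% to 5.4% of runs in every setting, close to the nominal 5%.

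**4. Price of the joint model.** On the plan's basis, mutual adjustment multiplies the information by 1 − r²:

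| r | Power at OR 1.50 | OR detectable at 80% | N for 80% at OR 1.50 |
|---|---|---|---|
| 0 | 80.2% | 1.50 | 299 |
| 0.2 | 78.6% | 1.51 | 311 |
| 0.3 | 76.4% | 1.53 | 328 |
| 0.5 | 68.2% | 1.60 | 398 |
| 0.7 | 51.8% | 1.76 | 586 |

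For example, at r = 0.5: √(300 × 0.16 × 0.75) × 0.4055 − 1.960 = 0.473, which gives 68.2%. The plan's P = 0.20 makes these figures conservative for 1:1 pairs. In the simulation, joint-model power for OAHI at OR 1.5 was 92.5% at r = 0.2 and 83.9% at r = 0.5.

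**The case against.** A reader might infer that SA1 cannot tell which subtype is associated with PAF at all. The documents do not support that. Each index gets its own odds ratio and 95% CI, unadjusted and adjusted, and that delivers what the aim promises for each index in turn. The independence named in the abstract is from cardiac structure, and left atrial volume and LVEF are in the covariate list. Only independence from the other subtype is missing.

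A reader might also infer that the study repeats the flaw it criticises in earlier work. It does not. Central apneas are scored separately, periodic breathing is scored, and CAI is a named exposure with its own model. The parallel fits the OAHI model alone, which does not take the central contribution into account.

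Three further points deserve weight.

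- *The size is assumed.* This stands: the effect vanishes at r = 0 and is small at 0.1.
- *Odds ratios of 1.08 to 1.41 lie below the 1.50 the plan can detect.* True, but 1.50 is the effect detected with 80% power, not the threshold for significance. On the plan's basis an estimate is significant above exp(1.960/√48) = 1.33, and step 3 shows how often smaller biases still give a significant result.
- *A joint model may not separate the subtypes cleanly.* This stands in part. Section 8 classifies apneas as central or obstructive but, in the text available, not hypopneas, and hypopneas count in OAHI. Any that are central in origin would remain there. That calls for a caveat, not for leaving the model out.

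**Conclusion.** The concern holds in a limited form. SA1 estimates each subtype's own association with PAF but cannot show which is associated independently of the other, although obstructive versus central is a named gap. These are secondary exposures described as exploratory, and the primary AHI analysis is unaffected.

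The size rests on an unknown correlation: none at 0, and a spurious odds ratio of about 1.08 to 1.41 per SD for r of 0.2 to 0.5 with a true odds ratio of 1.5 to 2.0 for the other index. With a true odds ratio of 1.5, the null index would be significant in about 11% of studies at r = 0.2 and 39% at r = 0.5, against about 5% in a joint model. The simulation assumes normally distributed exposures; a sparse or skewed CAI would behave differently. This is a cheap improvement to a secondary analysis, not a defect in the main result.

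**What to change.** Keep the separate models. In SA1 of sections 9 and 10:

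- Prespecify one further conditional logistic model containing OAHI and CAI together, with the same covariate sets.
- Fix the form of CAI in advance, for example log(CAI + 1), so that it is not chosen after seeing the data.
- Report the OAHI-CAI correlation.
- Label single-index odds ratios as not mutually adjusted, and base statements about independent subtype association on the joint model.
- State that OAHI includes hypopneas, and whether the scoring manual classifies these as central or obstructive.

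This needs no new data. The cost is one model and wider intervals, as shown in step 4: little up to a correlation of about 0.3, more beyond it. Power for CAI will be lower than shown if central events are sparse.

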a. Cardiac Structural Alterations. SDB leads to increased wall stress, increased afterload, increased atrial size ^{32, 33} and impaired diastolic function ^{32, 42}. Our published data demonstrate increased left ventricular mass index in SDB compared to those without SDB, mechanistically explained by the nocturnal degree of hypoxia ⁴³. Known risks for AF include increased left atrial volume and strain, left ventricular hypertrophy and left atrial wall motion velocity ⁴⁴, all which should be measured in any research on AF in SDB.

b. Systemic Inflammation. SDB markers include increased *interleukin-6 (IL-6)* ⁴⁵, *soluble IL-6 receptor (sIL-6R)*⁴⁶ and *high sensitivity C-Reactive Protein (hs-CRP)* ⁴⁷. Importantly, increased hs-CRP levels are implicated in atrial structural and electrical remodeling ^{48, 49} and increased IL-6 levels have been associated with AF ⁵⁰.

c. Oxidative Stress SDB-related intermittent hypoxia-reoxygenation results in oxidative stress ⁵¹⁻⁵⁴ which may alter myocyte ion channel function. Animal data show increased oxidized glutathione ⁵⁵ and NADPH oxidase levels in the left atrial appendage ⁵⁶ in persistent AF. Initiation and perpetuation of AF involves inflammation and oxidative stress, e.g. *endothelin-1* has been increasingly implicated as a pathogenic factor in AF resulting in upregulation of oxidative stress pathways ⁵⁷⁻⁵⁹. There are methods to quantify *F2-isoprostanes*, a recognized marker in SDB ⁶⁰⁻⁶² which are prostaglandin-like compounds derived from free radical-catalyzed peroxidation of arachidonic acid. This has allowed facile and accurate assessment of oxidative stress *in vivo* ⁶³ and will be measured in the current proposal.

3. A. 5. Sleep Disordered Breathing Potentially Accounts for Unexplained Atrial Fibrillation Risk: Clinical and Epidemiologic Data. The existing clinical and epidemiologic data in SDB are currently limited by a lack of objective assessments of cardiac and autonomic function ^{2, 64-67}, lack of consideration of central apnea ^{64, 67}, inconsistent arrhythmia adjudication (Sleep Heart Health Study), insufficient sample size ⁶⁶, retrospective data in a skewed population ²⁹ and the SDB data in AF studies depend largely on subjective measures (lack of objective sleep study data) ^{64, 68}.

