10. DATA ANALYSIS

EXPOSURES: *Primary:* 1) SDB defined by AHI, i.e. number of apneas + hypopneas/hour of sleep. *Secondary:* 1) Hypoxia: % sleep time with $\text{SaO}_2 < 90\%$, 2) Obstructive Sleep Apnea [obstructive apneas and hypopneas/hour of sleep, obstructive apnea hypopnea index (OAHI)], 3) Central Sleep Apnea [central apneas/hour of sleep, Central Apnea Index (CAI)], 4) Periodic Breathing and 5) EEG arousals [per hour of sleep, Arousal Index (AI)].

OUTCOME: 1) PAF (SA1) and 2) AF burden defined as frequency of AF paroxysms overall and based on self-reported sleep vs. wake (SA2 and 3)

COVARIATES: Age, race, body mass index (BMI, kg/m^2), waist circumference (cm), anti-arrhythmic/beta blocker/calcium channel blocker/ACE inhibitor/angiotensin receptor blocker medications, pacemaker, defibrillator, heart failure (NYHA class), BP, diabetes mellitus, left atrial volume, LVEF, caffeine use, alcohol use and smoking (current versus never smoker or pack years) and activity level. When assessing hypoxia as the relevant exposure, pulmonary disorders will be included as potential confounders.

Table 2. Mediator (SA1) or Outcome (SA3)

Domain	Primary	Secondary	Rationale
Echocardiographic Measures	Left Atrial Volume (ml/m^2)	LA Pressure, LA Systolic Strain, RA area, RA Pressure, LAA Peak Anterograde Flow Velocity (cm/s), Right Atrial Pressure (mmHg), LVEF, LVMI, LVH (concentric LVMI >0.41 , eccentric ≤ 0.41).	Left Atrial Volume predicts risk of AF and PAF ¹⁰³⁻¹⁰⁶ . Secondary measures also associated with AF.
Autonomic Function (Heart Rate Variability)	SDNN (ms) (Time Domain HRV Measure)	Time Domain (r-MSSD (ms), pNN50), Frequency Domain [LF (Hz), HF (Hz), LF/HF], Graphical Parameters (HR patterns, power spectral analysis, Poincaré plots and beat-by-beat HR tachograms) and Novel non-linear measures (e.g. Conditional Entropy ¹⁰⁷).	Reduced SDNN and LF/HF have been identified as AF triggers ⁴⁰ .
Systemic Inflammation	hs-CRP (mg/L)	IL-6 (pg/ml), sIL-6R (ng/mL)	hs-CRP and IL-6 associated with SDB and AF ⁴⁷⁻⁴⁹ . s-IL6R varies with overnight hypoxia ⁴⁶
Oxidative Stress	Endothelin-1 (pg/ml)	Urinary isoprostane 8-epi-prostaglandin F2a (ng/ mmolCr), Oxidized LDL (U/L)	Endothelin-1 implicated in AF ⁵⁷⁻⁵⁹ . Isoprostane ⁶⁰⁻⁶² and oxidized LDL sensitive to SDB ⁷⁶ .

ANALYTIC METHOD BY AIM.

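### The 84% power for the mediation aim describes a different design, and the mediator models state no correction for sampling on PAF status

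*Combined protocol and SAP*

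**What the plan says.** The Abstract sets the sampling: "Cases (PAF, n=150) will be recruited from our local AF clinics, and controls (n=150) from medicine and cardiology clinics". Subjects are therefore enrolled on PAF status, in equal numbers and individually matched.

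Section 10, Exploratory Aim 1a (repeated in Section 9) applies Pearl's mediation formula to the conditional logistic model. Of the mediator part it says "The approach involves a model for each mediator (e.g. a general linear model for a continuous mediator" and adds "possibly a random effect to account for clustering due to matching". It states that "This approach will allow a causally sound definition of the mediation effect of a given intermediate variable", and it fixes a decision rule: "If the CI does not contain zero, this will indicate statistically significant mediation". Neither section mentions sampling weights, a source prevalence or a controls-only mediator fit.

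The power text for Sub-Aim 1a (Sections 9 and 10) uses a difference in coefficients between two logistic models with SDB as AHI ≥ 15. It assumes a correlation of 0.9 between the adjusted and unadjusted estimates, PAF probabilities of 0.07 with SDB and 0.01 without, 150 per group, a mediated proportion of 0.5 and two-sided alpha 0.05, and it reports 84%. Its next sentence discusses imbalance between the SDB and non-SDB groups, so a group there means SDB status, not case status.

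**The concern.** The two parts are separate.

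**Power.** The calculation describes a sample drawn by SDB status in which few people have PAF. The study draws by PAF status, and half of its subjects have PAF.

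**Mediator models.** Pearl's formula needs the distribution of the mediator given SDB in the source population. A conditional logistic odds ratio tolerates case-control sampling. A linear model of a marker on SDB, fitted to cases and controls together, does not. If SDB and a marker are each related to PAF, over-sampling PAF makes them correlated in the sample even when SDB does not move the marker. Those conditions are the study's own premises: SA1 expects SDB to be related to PAF, and Table 2 selects markers because they are, for example "Left Atrial Volume predicts risk of AF and PAF". A random effect for pairs deals with clustering, not with sampling on the outcome.

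At stake is a marker being called a mediator when it is not, or, where SDB does shift it, its share being overstated.

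**Working it through.** **1. The plan's 84%.** Inputs are those of the Sub-Aim 1a power text.

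- Expected PAF patients: 150×0.07 + 150×0.01 = 10.5 + 1.5 = 12.
- Odds ratio: (0.07/0.93)/(0.01/0.99) = 7.45.
- Pooled risk-difference scale: SE = √(2×0.04×0.96/150) = 0.02263. SE of the difference between the two estimates = 0.02263×√(2×(1−0.9)) = 0.01012. z = (0.5×0.06)/0.01012 = 2.96. Power = Φ(2.96−1.96) = 84.2%.

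The figure reproduces. A Wald calculation on the log-odds scale gives 72.2%, but with 1.5 expected events in one group that approximation is poor. I use it only to show that the scale should be named.

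**2. The same formula for the actual design.** 150 cases and 150 controls; 30% SDB in controls (the plan's SA1 input), so 45 with and 105 without; correlation 0.9; half mediated; log-odds scale; matching ignored.

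Worked example at OR 2: case exposure odds = 2×45/105 = 0.857, so 69.2 cases with SDB and 80.8 without. SE = √(1/69.2+1/80.8+1/45+1/105) = 0.2420. SE of the difference = 0.2420×√0.2 = 0.1082. z = 0.5×ln 2/0.1082 = 3.20. Power = 89%.

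| SDB odds ratio | 1.5 | 2 | 2.13 | 3-4 |
|---|---|---|---|---|
| Power | 46% | 89% | 94% | >99% |

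The assumed correlation matters: at OR 2, power is about 62% with 0.8 and above 99% with 0.95.

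**3. Why pooling distorts the mediator model.** Take the limit of rare PAF, with a marker N(0,1) unrelated to SDB and an assumed marker odds ratio of 2 per SD. The case mean is then ln 2 = 0.693 and the control mean 0. At SDB OR 2.13, 71.6 cases and 45 controls have SDB, so 71.6/116.6 = 61.4% of SDB subjects are cases. Among non-SDB subjects it is 78.4/183.4 = 42.8%. The pooled fit shows a marker difference of 0.693×(0.614−0.428) = 0.13 SD where the truth is zero.

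**4. How often mediation is falsely declared.** Simulation: 150 cases, 150 controls, binary SDB (30% in controls), one marker independent of SDB, logistic outcome model, 95% interval for the product, 2,000 studies per cell and run. Entries are for assumed marker odds ratios of 1.5/2/3 per SD.

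| Source prevalence of PAF | SDB OR 2.13 | SDB OR 4 |
|---|---|---|
| 2.8% | 7/14/21% | 14/34/56% |
| 5% | 7/13/16% | 12/27/42% |
| 10% | 6/9/9% | 9/15/21% |
| 20% | 5/6/6% | 5/7/9% |

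Weighting cases by prevalence/0.5 and controls by (1−prevalence)/0.5 gives 4-6% throughout. A separate run at SDB OR 2.13 gave 6/16/22% at 2.8% and 5/5/6% at 20%, with about 4-8% after weighting.

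Closer to the plan (matched pairs, continuous AHI with OR 1.6 per SD, conditional logistic model, pair bootstrap), the random-effect mediator model gives 7/13/17% at 2.8% and 4/6/6% at 20%. The random effect does not remove the excess.

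**5. When SDB does move the marker.** With a 0.3 SD shift and total OR 2.13, true mediated shares of 16/28/44% are estimated as 19/34/54% at 2.8% (95% interval coverage 94/91/83%) and 17/29/47% at 20%. Dividing instead by the true total log odds ratio gives 21/39/65% at 2.8%.

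**The case against.** The strongest reply is that the size of the bias rests on two figures the documents do not give: PAF prevalence in the clinics that yield cases and controls, and the marker-PAF odds ratios. This stands. The 2.8% is 0.3×0.07 + 0.7×0.01, built from power inputs. Those inputs come from prior work whose limitations, according to the protocol's own Background, include "consideration of only nocturnal ECG data from the sleep study to ascertain AF". It is not a source prevalence, and the SA1 power text uses 0.20, where little goes wrong. The 56% in the table needs 2.8% prevalence, SDB OR 4 and marker OR 3 together.

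A zero SDB-marker link is also not the study's hypothesis; the Background argues that "SDB leads to increased wall stress, increased afterload, increased atrial size". In that case the problem is an overstated share, and imprecision is at least as large: intervals for the share were about 37/55/84 points wide. The text is a sketch that does not exclude weighting. That both pair members enter the mediator model is an inference from the possible random effect.

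Weighting is no complete cure. Section 11 (Recruitment and Informed Consent) lets controls come from an echocardiography database, selected on left ventricular function, and LVEF is a Table 2 measure. Section 7 (Follow-Up Visit) lets PAF patients be added from the sleep program because they have SDB; whether they enter SA1 is not stated. One prevalence weight undoes neither.

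On power, the formula gives 89% or more at the cited odds ratios, so the mismatch does no visible harm there.

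**Conclusion.** Both parts hold, with limits. The 84% is correct arithmetic for a design the study does not have and should not stand as its power. A reader might infer that the aim is underpowered. The documents do not support that: on the plan's formula and correlation, power falls short only below the cited range of odds ratios (46% at 1.5).

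The mediator models state no correction for sampling on PAF, and the pair random effect does not supply one. If PAF is a few percent of the source population and the marker is moderately to strongly related to PAF, the interval rule exceeds its 5% error rate (about 6-22% at 2.8% prevalence, SDB OR 2.13, assumed marker OR 1.5-3 per SD) or the mediated share is overstated. At about 20% prevalence the effect is small. A reader might infer that any mediation finding will be false; that goes too far, because neither the prevalence nor the marker odds ratios are known. The aim is exploratory and SA1 is unaffected. Severity: minor to moderate.

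**What to change.** 1. Replace the 84% sentence with power for 150 cases and 150 controls, 30% SDB in controls and SDB odds ratios spanning 2-4. Name the scale and the correlation assumption.
2. In Aim 1a, report beside the unweighted fit a mediator model on all subjects, weighted to an assumed source prevalence over a range (e.g. 1-20%), with matching factors as covariates and whole pairs bootstrapped. Do not declare mediation from the unweighted interval alone when the weighted results disagree.
3. Exclude from Aim 1a any cases recruited through the sleep program. Do not interpret mediation by LVEF or other left ventricular measures for controls selected on left ventricular function.

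This costs a SAP paragraph, a weight variable and extra runs; it needs no new data. There are two statistical costs, which is why the weighted fit is reported beside the unweighted one and does not replace it.

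- **Precision.** The mediator-slope SE is about 1.1-1.5 times larger. Power for a 0.3 SD marker shift (SDB OR 2.13, marker OR 1.5/2/3) falls from 76/91/93% to 38/42/41% at 2.8% prevalence, where the unweighted figures include the bias. At 20% it falls from 70/79/80% to 51/59/61%.
- **Reliance on an assumed prevalence.** If the truth is 5% and 20% is assumed, false positives at SDB OR 2.13 are 5/8/10%, against 7/13/16% unweighted.
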